**CONFIDENTIAL**

056-F275, vC Clinical Investigation Plan Template

# CIP339 Clinical Investigation Plan

D00456959

Version F

Page 91 of 93

Medtronic

Version	Summary of changes	Justification of changes	Potential impact of the change on performance, effectiveness, or safety or other endpoints	Identification of the affected study documents	Author(s)/Title
D	

See "Attachment 1: CIP339 Description of Protocol Changes Version C to D" for details on changes

Added product (Klue Health App release tag 2.0) and clarification for endpoint analysis

Increased number of subjects to enroll and complete

Increased duration of subject participation

Added subject repeat participation

Increased overall study duration

Adjusted visit days and visit windows for Visit 2 through Visit 7

Updated meals for at-home baseline and in-clinic meal challenge

Added device re-use disclosure

Typo/formatting/wording corrections throughout document

	

To add product for use in the study

To allow for more subjects and subject repeat participation in the study

To optimize visit days and visit windows

To include additional meals/beverages during the meal challenge

To clarify device re-use

To correct/clarify CIP language

	

Clarifications made to endpoints

	

Updates required for informed consent and investigator's brochure

	
[REDACTED] Sr. Medical Writer

*Medtronic Business Restricted*

**CONFIDENTIAL**

056-F275, vC Clinical Investigation Plan Template

# CIP339 Clinical Investigation Plan

D00456959

Version F

Page 92 of 93

Medtronic

Version	Summary of changes	Justification of changes	Potential impact of the change on performance, effectiveness, or safety or other endpoints	Identification of the affected study documents	Author(s)/Title
E	

See "Attachment 1: CIP339 Description of Protocol Changes Version D to E" for details on changes

Typo/formatting/wording corrections throughout document

Added product [REDACTED]

Revised device re-use disclosure

	

[REDACTED]

To correct/clarify CIP language

To clarify device re-use

	

None

	

Updates required for informed consent

	Sr. Medical Writer

*Medtronic Business Restricted*

**CONFIDENTIAL**

056-F275, vC Clinical Investigation Plan Template

# CIP339 Clinical Investigation Plan

D00456959

Version F

Page 93 of 93

Medtronic

Version	Summary of changes	Justification of changes	Potential impact of the change on performance, effectiveness, or safety or other endpoints	Identification of the affected study documents	Author(s)/Title
F	

See "Attachment 1: CIP339 Description of Protocol Changes Version E to F" for details on changes

Updated "Duration"

Updated "Schedule of Events"

Removed breakfast meal challenge on Day 4 (at home and in-clinic)

Updated window for Visit 3

Updated questionnaire timing

Updated "Table 4. Study Visit Details"

Typo/formatting corrections throughout document

	See "Attachment 1: CIP339 Description of Protocol Changes Version E to F" for details	Updates required for informed consent		Sr. Medical Writer

*Medtronic Business Restricted*

**CONFIDENTIAL**

056-F275, vC Clinical Investigation Plan Template

In patients with insulin dependent diabetes mellitus, glycemic control is influenced by numerous factors, such as insulin dosage, insulin absorption, timing, and physiological/ lifestyle factors such as exercise, food intake, hormones and illness. These factors may contribute to significant variability in insulin requirements, which makes self-management of type 1 diabetes challenging.

Patients who are using continuous glucose monitoring, including sensor-augmented pump therapy, experience improvements in glycemic control. Advanced features of sensor-augmented pump therapy are now being used in clinical practice; these include automatic suspension of insulin delivery when a pre-set glucose threshold is reached (low glucose suspend) or is predicted to be reached (predictive low glucose suspend). Both approaches have shown that a significant reduction in the risk and burden of hypoglycemia can be achieved, especially in patients who are prone to experiencing hypoglycemia.

Medtronic's latest system is the MiniMed 780G system, also referred to as the Advanced Hybrid Closed Loop (AHCL) system, a self-adjusting basal insulin pump with autocorrection dosing. Patients using the MiniMed 780G system are not required to confirm sensor glucose using a self-monitored blood glucose (SMBG) measurement before making therapy adjustments based on displayed sensor glucose values. Patients are still required to enter manual meal announcements (grams of carbs). With burden reduction in mind, the next generation of the AHCL system is focused on automated meal gesture dosing thereby eliminating the need for manual meal announcements.

Meal gesture dosing is a mode whereby meal announcements are not entered manually by the user. Instead, when meal gesture dosing is active, meal announcements are generated automatically by the system based on the detection of eating gestures. Eating gestures are derived from analyzing the motion sensor data from the user's Apple Watch (worn on the user's hand of eating). When eating is detected, the system translates the detected eating activity into an equivalent carb amount that is sent to the pump as a meal announcement. Sensor glucose based safety guardrails and rate control help ensure that automatic generation of meal announcements is safe.

The purpose of this study is to evaluate subject safety of using the Klue Health app utilizing meal gesture micro insulin dosing (meal gesture dosing) within the AHCL system in adult subjects with type 1 diabetes in a clinic setting.

4. Study Objectives

The objective of the study is to collect data for meal gesture dosing for unannounced meals within the AHCL system to be used for development of Medtronic Diabetes devices and products.

5. Investigation Plan

This study is a single-center, single arm study in adult subjects with type 1 diabetes utilizing AHCL System with meal gesture detection and micro dosing (meal gesture dosing). Meal gesture dosing is a mode whereby meal announcements are not entered manually by the user. Instead, when meal gesture dosing is active, meal announcements are generated automatically by the system based on the detection of eating gestures and micro doses of insulin are given.

Overall subject participation will be approximately 3 weeks to 4 months.

- A total of up to 40 subjects (aged 18-75) may be enrolled at one investigational center in Israel to have at least 16 subjects complete the study. Subjects may repeat participation at the request of the Sponsor and at the discretion of the investigator but will only be counted once toward the total number of subjects.

6. Determination of Sample Size

Given that this study is not statistically powered, no sample size calculation was performed. A total of up to 40 subjects will be enrolled at one investigational center in Israel to have at least 16 subjects complete the study. Subjects may repeat participation in the study at the request of the Sponsor and at the discretion of the investigator but will only be counted once toward the total number of subjects.

7. Statistical Methods

7.1 Study Subjects

7.1.1 Disposition of Subjects

The number of subjects enrolled, completed, early terminated the study will be presented. The reasons for discontinuing prior to study completion will be summarized.

7.1.2 Clinical Investigation Plan (CIP) Deviations

All protocol deviations will be presented in the listings.

7.1.3 Analysis Sets

All enrolled subjects who have participated in the study will be included in the efficacy analysis population. All enrolled subjects will be included in the safety analysis population.

7.2 General Methodology

All data collected from the time of screening until the end of the study will be collected either on eCRFs or electronically by uploading the various devices. Data and analysis will be summarized in a Clinical Study Report.

7.3 Center Pooling

Not Applicable.

7.4 Handling of Missing, Unused, and Spurious Data and Dropouts

In determining the phase of adverse events and protocol deviations or in calculating the duration of diabetes, the first day of the month will be used for event dates with known year and month but unknown day, unless specified otherwise in the description; similarly, the first day of the year will be used for event dates with known year but unknown month and day, unless specified otherwise.

All available data will be included in the data listings and tabulations. No imputation will be applied for the missing data.

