**Figure 3. Visit Schedule**

The study is comprised of a run-in period of approximately 1 week to 3 months and a study period of approximately 10 days.

Prior to study start, Investigator or authorized designee must obtain written informed consent from the patient before any clinical study related activity (including screening) takes place and document informed consent process in the medical chart of the patient (refer to **Section 10.11 Subject Consent**).

Study staff will discuss with the participant the visit schedule and will make arrangements with the subjects for the contacts at investigational center and sponsor. Participants who are not compliant with the arranged contacts, which may impact patient's safety, may be discontinued at the discretion of the investigator.

Subjects will be using the Klue Health app and Apple Watch. The subject must wear the Apple watch on the wrist of the hand used for eating for the duration of the study.

Subjects will also be using the [REDACTED]

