#### **Study Period – 5 days (4 nights) In-Clinic:**

After the run-in period and completion of the 5-day at-home study period with baseline meal challenges, study subjects will check into the clinic for a 5-day (4 nights) intervention.

Study subjects will be asked by investigational center staff to consume meals of the same size and content they consumed for the meal challenges during the baseline meal challenge (at-home study period). For example: If a large sized dinner meal with low carbohydrate content was consumed at 5 pm on Day 1 during the baseline meal challenge, that same dinner meal should be consumed at approximately the same time on Day 1 of the in-clinic study period. Subjects will be asked by investigational center staff to check BG at the start of the meal, as well as 2 hours and 4 hours after the start of the meal and provide correction as necessary. All meals consumed during the in-clinic study period should be logged in the FoodPrint app.

Subjects will be instructed by investigational center staff to not use the pump's meal bolus calculator (no manual meal announcements) for the duration of the intervention.

Scheduled meal challenges during the study period (mirror baseline meal challenge):

- Day 1: long meal with low carb count (lunch) and large meal with low carb count (dinner)
- Day 2: small meal with high carb count (lunch)
- Day 3: large drink with no carbs (breakfast) and typical meal size with medium carb count (dinner)
- Day 4: long meal with high carbs (lunch)
- Day 5: large drink with high carb (breakfast) and typical meal size with low carb count (lunch)

On Day 5 of the in-clinic meal challenge, a subject may be asked to repeat a specific meal challenge which may require the subject to participate for an additional day.

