### **10.3.2 Study Period – In-Clinic: Meal Challenge**

#### **10.3.2.1 Visit 7: Start In-Clinic, Day 7 (window of +10 days)**

##### **10.3.2.1.1 Day 1**

The investigational center staff will:

- Activate automated meal gesture dosing feature in Klue Health app and confirm that system is working
- Instruct subject to eat:
  - Long meal with low carbohydrate count (lunch): A timed meal that is smaller in carbohydrates than a regular lunch meal for an individual study subject.
  - Large meal with low carbohydrate count (dinner): A large meal consists of meal that is larger in size, but smaller in carbohydrates than a regular dinner meal for an individual study subject.
- Ask subject about adverse events or device deficiencies

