
Risk with Closed Loop Therapy with Meal Gesture Dosing
 
The risks associated with using the insulin pump in closed loop mode with meal gesture dosing are related to the potential for delivery of too much or too little insulin which can result in:
 
 
Hypoglycemia
 
Severe hypoglycemia
 
Hyperglycemia
 
Diabetic ketoacidosis
 
User entry error 
 
Patient entering false glucose values for any reason leading to hypoglycemia and hyperglycemia
 
Patient entering false BG values for calibration leading to hypoglycemia or hyperglycemia
 
 
 
Sensor failure resulting from patient failure to calibrate leading to hypoglycemia or hyperglycemia
 
Sensor over-reading resulting in hypoglycemia
 
Sensor under-reading resulting in hyperglycemia
 
Sensor missed transmission, or any other fault resulting in no SG value, leading to hyperglycemia or hypoglycemia
 
Voluntary insulin delivery (with the pump or with a syringe) immediately prior to entering Auto Mode may result in severe hypoglycemia despite shutting down insulin delivery by the algorithm
 
Hypoglycemia related to patient taking insulin via injection while in Closed Loop (Auto Mode)
 
Hypoglycemia or hyperglycemia related to entering or exiting Closed Loop (Auto Mode)
 
Insulin over-delivery due to potential interference from acetaminophen
 
Cyber security hacking into pump
 
	
Prevention and Mitigation
 
Prevention and mitigation include:
 
 
Closed Loop Therapy with meal gesture dosing will only be active during the in-clinic portion of study period. Subjects will be under constant surveillance by investigational center staff.
 
Follow the provided user guides for insulin pump management.
 
Train prior to study device use on appropriate device use and diabetes management principles and told to call with problems and instruct to call investigator with problems.
 
Instruct to check their meter glucose if their high or low symptoms do not match their sensor alerts or sensor glucose readings in order to make diabetes treatment decisions.
 
Instruct to check their meter glucose if there are any concerns that the sensor glucose value is not accurate.
 
Instruct if there are no sensor values, no treatments decision will be made until a BG is confirmed.
 
Instruct to have glucose on hand for hypoglycemia.
 
Instruct to avoid the use of products containing acetaminophen
 
If acetaminophen is taken, subjects will be instructed to use additional BG meter readings (they are not to calibrate with those readings) to verify their glucose levels.
 
If acetaminophen is taken, subjects will turn off Auto Correction and exit Auto Mode
 
Pump has cybersecurity encryptions to prevent hacking.
 
Instruct subjects to keep their own insulin pump supplies in a safe place and to have back up supplies in the event they are asked to revert back to their own therapy during the study
 

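### Minor, cheap to fix: within one participation, the SAP's first-of-month rule for partial dates can move an adverse event out of the in-clinic gesture-dosing phase but never into it

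*SAP*

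**What the plan says.** SAP 7.4 gives one rule for incomplete dates and states its use: "In determining the phase of adverse events and protocol deviations or in calculating the duration of diabetes". For those purposes, "the first day of the month will be used for event dates with known year and month but unknown day", and likewise "the first day of the year will be used for event dates with known year but unknown month and day". Each half allows for exceptions specified elsewhere, but neither document specifies any. Nothing stops the imputed date from falling before consent, before devices are dispensed or before the phase in which the event was reported. Neither document defines the phases for adverse events.

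The sequence of periods comes from the protocol. Section 10.1 describes "a run-in period of approximately 1 week to 3 months and a study period of approximately 10 days". After run-in and the at-home baseline week, "study subjects will check into the clinic for a 5-day (4 nights) intervention"; repeating a meal challenge may add one day. Visit 7 is set for Day 7 and may start up to 10 days later (10.3.2.1). Table 5 in section 11.1 says that "Closed Loop Therapy with meal gesture dosing will only be active during the in-clinic portion of study period". The study ends at Visit 7 (10.8), and adverse events are recorded only while the subject is enrolled (12.2). Within one participation, no phase follows the clinic stay.

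**The concern.** The first of the month is never later than the true date, so the rule moves dates backwards or leaves them alone. In a design where exposure starts early and continues, that can be a cautious default. Here the exposure of interest comes last and lasts 5 days, after a run-in of up to about 3 months. An event with an unknown day therefore tends to be filed under run-in or the at-home period, when the app was only monitoring.

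The study's stated purpose is to evaluate the safety of gesture dosing (protocol 4.2, repeated in the SAP). If events are shown by phase, the error runs one way within a participation, and that way favours the investigational mode. With a target of at least 16 completers, a by-phase table may hold so few events that one misfiled event is visible.

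**Working it through.** The plan gives no figure to reproduce, so the check applies the rule to the calendar.

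**Inputs.** From the documents: a 5-day stay, or 6 with the extra day; Visit 2 on Day -6 and Visit 7 on Day 7, so 13 days apart on the nominal schedule; Visit 7 up to 10 days later; run-in of about 1 week to 3 months. Assumed: stay start dates and event days are uniform; run-in is 7, 30 or 90 days; consent is 7 days before run-in. The enumeration covers 1,461 start dates (4 calendar years). The mean month is 1461/48 = 30.44 days.

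**Direction.** No imputed date was later than the true date in any scenario. No event from an earlier period of the same participation was moved into the stay.

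**Share keeping the right phase, day unknown.** An event on stay day k stays in the phase only if a first of the month falls on stay days 1 to k. The probability is k/30.44.
- 5-day stay: mean k = 3, so 3/30.44 = 9.9% stay and 90.1% leave.
- 6-day stay: mean k = 3.5, so 3.5/30.44 = 11.5% stay and 88.5% leave.

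The enumeration gives the same figures.

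**Where they land (5-day stay, % of day-unknown in-clinic events).**

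| Run-in, delay to Visit 7 | In-clinic | At-home | Run-in | Consent to run-in | Before consent |
|---|---|---|---|---|---|
| 7 days, none | 9.9 | 19.7 | 23.0 | 23.0 | 24.4 |
| 7 days, 10 days | 9.9 | 52.6 | 23.0 | 14.6 | 0 |
| 30 or 90 days, none | 9.9 | 19.7 | 70.4 | 0 | 0 |
| 30 or 90 days, 10 days | 9.9 | 52.6 | 37.6 | 0 | 0 |

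The before-consent column depends on the assumed consent date.

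**Share dated before devices are dispensed.** If Visit 2 is D days before Visit 7, the imputed date precedes Visit 2 when the calendar day exceeds D + k.
- D = 13: (30.44 - 13 - 3)/30.44 = 47.4%.
- D = 23: (30.44 - 23 - 3)/30.44 = 14.6%.
- D of 30 or more: 0%, because the first of the month is at most 31 - 1 = 30 days before stay day 1.

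**Month and day unknown.** 3/365.25 = 0.8% stay in the phase (5-day stay). Between 68% and 94% are dated before consent across the scenarios.

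**Repeat participation.** If a second participation starts within about 2 weeks of the first stay, about 16% of its day-unknown run-in and at-home events are moved back into that first stay (5/30.44 = 16.4%). At a 4-week gap this is about 1%.

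**Cost of the opposite rule.** Suppose an event is called in-clinic whenever its known month overlaps the stay. All true in-clinic events are kept. An event j days before the stay is also pulled in unless a month boundary lies between; over j = 1 to 13 the mean j is 7, so 1 - 7/30.44 = 77.0%.

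**The case against.** The strongest objection is that the triggering case should hardly occur. In clinic, subjects are under constant surveillance (protocol 11.1) and are asked about adverse events on each of Days 1 to 5 (10.3.2.1). Start and end dates are to be documented for every event (section 12). The 90% is conditional on an unknown day, and the documents give no basis for estimating how often that happens. This stands, and it keeps the point minor.

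Three stronger inferences are tempting and are not supported:
- **The safety endpoints are biased.** They are counts of events (SAP 7.9.2), summarised over all enrolled subjects (SAP 7.10). Attribution to the device rests on relatedness, judged by investigator and sponsor (protocol Table 7 and 12.4), with committee review of serious events, severe hypoglycemia and DKA (13.1). ADE, SADE and USADE counts do not use the imputed phase, and no by-phase safety table is specified.
- **Events dated before consent drop out.** No rule removes them. SAP 7.4 keeps all available data in listings and tabulations, and SAP 7.1.3 puts every enrolled subject in the safety set.
- **Events can never enter the in-clinic phase.** This is true only within one participation; repeat participation is an exception.

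It is also fair to object that assigning every ambiguous event to the clinic stay creates the opposite error. Partial dates are likelier for events at home, so that rule alone could misfile more events than it rescues.

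**Conclusion.** The point holds as a minor one. SAP 7.4 plans to assign adverse events to a phase, and the rule it states gives the wrong phase for about 90% of in-clinic events with an unknown day (88.5% for a 6-day stay). Within a participation the error is one-way, out of the gesture-dosing phase. These percentages assume uniform start dates and event days; the direction needs no assumption. The share dated before device dispensing runs from about 47% on the nominal schedule to 0% when Visit 2 is 30 days or more before Visit 7, so 47% should not be read as typical.

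The number of events affected is probably very small. Total and relatedness-based safety counts stand. What is at risk is any statement that an event occurred before, rather than during, gesture dosing. The rule is worth changing because the change is cheap and that distinction bears directly on the study's purpose.

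**What to change.** Amend SAP 7.4 for phase assignment only:
1. Never impute a start date before informed consent for the relevant participation.
2. First use the other recorded information, namely the visit at which the event was reported and its end date, to narrow the possible dates.
3. If the event is still compatible with the in-clinic period, assign it there and flag it as imputed in the listing.
4. If any by-phase safety table is produced, show the counts with and without flagged events.

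Keep the first-of-month rule for duration of diabetes, where this problem does not arise.

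The cost is one SAP paragraph and a flag variable, with no new data and no change to study conduct. The downside is the 77% shown above: on the month alone, most day-unknown events from the 13 days before the stay would be assigned to gesture dosing. Step 2 should reduce that share, since an event reported before activation cannot be in-clinic. The flag and the two-way count let a reader see what remains.

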7.5 Adjustments for Multiple Comparisons

No adjustments will be made.

7.6 Demographic and Other Baseline Characteristics

Subject demographics and baseline characteristics will be summarized by descriptive statistics (mean, standard deviation, minimum, median, and maximum) for continuous variables and by counts and percentages for categorical variables.

7.7 Treatment Characteristics

The AHCL system with Meal Gesture Dosing evaluated in this study includes a commercial/CE-Marked insulin pump with investigational software and both CE-marked and investigational components, which will all be used as described in labelling and instructions for use for which CE mark has been obtained (as applicable). The AHCL system will also include the addition of the Klue Health mobile app with investigational software (installed on Apple Watch) for meal gesture detection and micro dosing. The AHCL system without meal gesture dosing is indicated for management of type 1 diabetes.

